7. EXPECTED RESULTS

The Hypotheses – It is expected that:

- The study will be able to produce data in order to design a larger, funded study
- Patients will express comfort in using home telemonitoring
- The pharmacists will be able to collect and monitor hypertension data using mobile health technology
- A statistically significant ($p < 0.05$) greater proportion of patients in the after study period will be in proper control of their hypertension ($< 130/80$ mmHg) than in the before study period

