4. STUDY DESIGN

This is a pragmatic before and after trial with the patient serving as their own control

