5. STUDY POPULATION

We are aiming to enroll 20 patient participants for this pilot study. To be eligible for participation, enrollees must be ≥ 18 years old, have a smartphone compatible with the mobile intervention, have been previously diagnosed with hypertension, have uncontrolled hypertension (SBP > 130 mmHg and/or DBP > 80 mmHg), be under the care of a primary care physician in the Family Medicine

Department of the USF Morsani Center for Advanced Care, have had at least one prescription filled at Pharmacy Plus within the last six months, and speak English fluently.

Patients will be excluded if they are already under the care of a clinical pharmacist in the Family Medicine department, are pregnant, or have a serious existing medical condition(s) that may affect their ability to self-monitor their blood pressure (for example, stroke, dementia).

Recruitment

A list of potential patients (Family Medicine patients with diagnosis of hypertension who have had at least one prescription filled at Pharmacy Plus within the last 6 months) will be generated by the Epic support team and identified through the electronic medical records system as well as the pharmacy prescription database. The pharmacists from Pharmacy Plus on this study or 4th year pharmacy students on their Ambulatory Care or Community Pharmacy Rotation will call patients on this list and will discover if the patient meets the final qualification for the study (has a smart phone or other smart device) and is interested in being a part of the study. This is not cold calling, as this list includes eligible patients who have had a prescription filled at Pharmacy Plus within the last 6 months. Each patient on this list has interacted with the pharmacists at Pharmacy Plus when the medication was dispensed. The pharmacists have an established relationship with these patients, as they are involved with the care of these patients. They are involved with the treatment of these patients as they provide pharmacy services when dispensing medications and counseling the patients, as well as some medical services such as vaccine administration.. [name], who practices in the Family Medicine department, is the physician on this study and is aware that these patients will be contacted via phone. We will not be obtaining verbal consent to participate during this phone call.

Enrollment

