11. DATA MANAGEMENT AND ANALYSIS

- Primary Objective: Preliminary data to design a larger, funded study
 - Captured data and information will be collected in such a way as to make it useful for putting forth a cogent argument for a larger effort.
- BP readings will be captured automatically in Epic
- Mean BP readings will be calculated and compared for the pre- and post-periods, as will the number of patients in and out of blood pressure control
- Pre- and post-study data will be analyzed using a comparison of means (2-tail t-test) and chi-square for comparing low compliant patients (for using the devices) with high compliant patients. The post-study patient satisfaction data will be analyzed using descriptive statistics.

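### The only blood pressure hypothesis with a numerical criterion is p < 0.05 on control dichotomised at 130/80 in about 20 patients; the already planned comparison of mean BP should carry the hypothesis, with its SD and a 95% CI

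*Combined protocol and SAP*

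**What the plan says.** Section 4 describes a single-group, paired design: "This is a pragmatic before and after trial with the patient serving as their own control". Section 5 gives the target, "We are aiming to enroll 20 patient participants for this pilot study", with no power or precision rationale, and requires that entrants "have uncontrolled hypertension (SBP > 130 mmHg and/or DBP > 80 mmHg").

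Section 3 makes preliminary data for a larger study the primary objective. Whether BP readings improve is the last of three secondary objectives.

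The last bullet of Section 7 is the only BP hypothesis with a numerical criterion: "A statistically significant ($p < 0.05$) greater proportion of patients in the after study period will be in proper control of their hypertension". The bullet sets the cut-off for control at 130/80 mmHg and takes the before period as the comparator.

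Section 11 goes further than that hypothesis: "Mean BP readings will be calculated and compared for the pre- and post-periods", along with the numbers in and out of control. On tests it says "Pre- and post-study data will be analyzed using a comparison of means (2-tail t-test) and chi-square for comparing low compliant patients". The chi-square reads most naturally as belonging to the compliance comparison, so no test is clearly assigned to the before/after proportion. No SD or confidence interval is mentioned for the BP change.

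**The concern.** A yes/no status at 130/80 discards most of each patient's change. A fall from 150 to 135 counts as nothing, and one from 131 to 129 can count as a success. In 20 patients the resulting count is coarse, so only a large observed gain can reach p < 0.05.

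This matters because of the pilot's purpose. A larger study needs an estimated change, its SD and an interval. A p-value on a dichotomy gives none of these. Because only large observed gains can be significant, a control gain reported on that ground may also be too optimistic as a planning value.

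**Working it through.** **Inputs from the plan.** n = 20 (Section 5); paired data (Section 4); alpha 0.05 and control < 130/80 (Section 7); entry above essentially the same cut-off (Section 5). If the before status is the status at entry, about 0 of 20 are controlled before. The plan does not otherwise define the before period. It states no power, effect size or SD, so there is no figure of its own to reproduce.

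**Step 1: smallest significant result from 0/20 controlled.** Let g be the number who gain control, with none losing it.
- Exact McNemar, two-sided: p = 2 × 0.5^g. g = 5 gives 0.0625; g = 6 gives 0.031. Needs 6/20 = 30 points.
- Exact McNemar, one-sided: p = 0.5^g. g = 5 gives 0.031. Needs 5/20 = 25 points.
- Fisher (ignores pairing): 5/20 gives 0.047. Needs 25 points.
- Uncorrected McNemar: chi-square = (gains − losses)²/(gains + losses) = g. g = 3 gives 0.083; g = 4 gives 0.046. Needs 4/20 = 20 points.
- Uncorrected Pearson chi-square (ignores pairing): 40 × (20 × 4)² / (20 × 20 × 4 × 36) = 4.44, p = 0.035. Needs 20 points.

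If any patient loses control, the bar rises. With exact McNemar, 7 gains and 1 loss give 0.070, so 8 and 1 are needed, a net 7/20 = 35 points.

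**Step 2: power and mean observed gain given significance.** X ~ Binomial(20, true conversion), significant if X ≥ k, no losses.

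| True conversion | Power, k = 4 | Power, k = 5 | Power, k = 6 | Mean significant gain, k = 4 | Mean significant gain, k = 6 |
|---|---|---|---|---|---|
| 20% | 0.59 | 0.37 | 0.20 | 25.9% | 33.4% |
| 30% | 0.89 | 0.76 | 0.58 | 32.0% | 36.9% |
| 40% | 0.98 | 0.95 | 0.87 | 40.4% | 42.6% |
| 50% | 1.00 | 0.99 | 0.98 | 50.0% | 50.6% |

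Power passes 50% at a true conversion of about 18% (k = 4), 23% (k = 5) or 28% (k = 6).

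**Step 3: the same fall on both outcomes.** The documents give no BP distribution, so these are assumptions: baseline SBP mean 136 to 140 (SD 10), DBP 82 to 84 (SD 7), correlation 0.5; SD of change 9 and 6, correlation 0.6; n = 20. For mean SBP change, the paired t-test at a 6 mmHg fall has noncentrality 6/9 × √20 = 2.98 and power of about 0.81. Control-test power is simulated, so the last digit varies between runs.

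| True fall | Before status | Exact McNemar | Uncorrected McNemar | Paired t, SBP |
|---|---|---|---|---|
| 6/3 | some controlled (about 9–17%) | 12–17% | 39–41% | about 80% |
| 6/3 | nobody controlled | 21–46% | 61–81% | about 80% |
| 10/5 | some controlled | 44–52% | 74–77% | over 99% |
| 10/5 | nobody controlled | 61–84% | 91–98% | over 99% |

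At 6/3 with exact McNemar, the mean observed gain given significance is 33 to 36 points, against a true 17 to 27.

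**Step 4: sensitivity to starting BP.** A separate simulation used the 6/20 rule, SBP falls of 5 to 10 mmHg and a DBP fall of 0.6 times the SBP fall. Power was 0.31 to 0.91 at about 139–141/83, 0.05 to 0.45 at about 144/86, and under 0.05 at about 151/90.

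**Step 5: what the mean change delivers.** The 95% CI half-width is 2.093 × SD/√20 = 0.468 × SD: 4.7, 5.6 and 7.0 mmHg for assumed SDs of 10, 12 and 15. A paired t-test has 80% power for a fall of 6.6, 7.9 and 9.9 mmHg at those SDs.

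**The case against.** The strongest reply is that Section 11 already compares mean BP with a t-test. A reader of Section 7 alone might infer that the pilot as a whole would report no effect when BP has fallen. The documents do not support that: the planned t-test could detect the same fall. This stands, and it limits the point to which outcome carries the hypothesis and to the missing SD and interval.

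Second, Section 7 lists expected results. It sets no go/no-go rule, BP is a secondary matter, and nothing says that the control gain alone will feed the larger study. This also stands, and lowers the stakes. It does not make the dichotomy a better hypothesis.

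Third, the power figures turn on the test and the baseline. A reader might infer that a real fall will usually be missed. That is too strong: with nobody controlled before, a 10/5 fall is found 61 to 84% of the time even by the exact test, and the uncorrected test at 6/3 can match the t-test. A reader might also infer that any significant result must overstate the gain. That is certain only when the true gain is below the smallest significant one. At a true 40% the average excess is 0.4 to 2.6 points, and at 50% it is under 1 point.

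Finally, selection above the cut-off produces some apparent gain with no effect at all (about 1 to 10% conversion in the Step 4 simulation with an assumed visit-to-visit SD of 8 mmHg). Mean change shares this bias (0.3 to 1.8 mmHg there), so moving the hypothesis does not cure it.

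**Conclusion.** The point holds in a conditional form. The one BP hypothesis with a numerical criterion rests on the less informative of two outcomes that the plan already collects. From nobody controlled, it needs 4 to 6 converters in 20, depending on the unassigned test.

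Over the assumed distributions, the gap in power at a 6/3 fall runs from very large (12% against about 80%) to none (81% against about 80%). A moderate fall may often be missed on this hypothesis, most readily when patients start well above 130/80 or when the exact test is used. Overstatement of a significant control gain is material when the true gain is below or near 20 to 30 points and minor from about 40 points up.

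The thresholds in Step 1 follow from n = 20 and the choice of test. The power figures rest on assumed means, SDs and correlations, on 20 completers, and on what the before period means.

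**What to change.** Reword the last bullet of Section 7 along these lines: *Mean SBP and mean DBP will be lower in the after period than in the before period, estimated as the mean within-patient change with its SD and 95% CI.*

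In Section 11, add the SD and 95% CI of the within-patient change to the planned comparison of means. Keep the number of patients < 130/80 before and after as a descriptive result, with a 95% CI for the paired difference and no significance criterion.

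This changes one bullet and about one line and needs no new data. The price is that the pilot can no longer headline a significant improvement in control.

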Patients interested in participating in the study will be scheduled for a one-hour in-person appointment at the clinic site, where they will be asked for consent for participation in the study. The informed consent process will be completed by the study coordinator or a study pharmacist, (all who have successfully passed CITI training) in a face-to-face session with the patient. The pharmacist will explain the consent form in detail, with opportunities along the way for the patient to ask questions. The pharmacist will check, at proper points, for confirmation of understanding.

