6. INTERVENTIONS

Devices

- Smart Phones with Apple Health Software will be used to monitor blood pressure once a day, and results will be sent automatically to the patients EHR (Epic)
- The Omron 10 Series Wireless Upper Arm Blood Pressure Device will be given to the patient to monitor blood pressure at home daily

Pre- and Post-surveys

- A pre- and post-survey will be given at the initial and final in-person appointments, respectively
- These surveys will collect basic patient demographics, knowledge of blood pressure, comfort with checking blood pressure at home, and previous experience working with a pharmacist

Pharmacist Management

- Review of evidence-based therapy and recommendations for improvement if needed
- Educate the patients on how to monitor their blood pressure with their Bluetooth enabled home blood pressure monitor and smart phones

- Patients will be scheduled for a one-hour in-person appointment for the initial study visit where informed consent will be obtained, and for the final study visit
 - At the final study visit, the patients will complete a post-study survey and be given a \$25 gift card upon return of the blood pressure device
- Review results once per week
 - If any patient has an SBP reading > 160 mmHg or DBP > 100 mmHg, they will be instructed to wait five minutes and then recheck their BP. If the BP readings exceed these thresholds for three days in a row, the patients should contact their primary care provider in the clinic for further management.
 - If SBP > 180 mmHg and/or DBP > 120 mmHg, patients will be instructed to call 911 or have someone drive them to the ER immediately
 - There will not be alerts sent to the study pharmacists if the blood pressure readings are above these thresholds
- Follow-up with patients once per week for six (6) weeks via scheduled 20-minute telehealth appointment with each patient via the HIPAA secure and compliant platform, VSee
 - During this telehealth appointment, the study pharmacists will counsel the patients on their blood pressure readings for that week and provide lifestyle education focusing on patient-specific diet and exercise recommendations
- The total duration of the study will be eight (8) weeks

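### The before-period blood pressure is not defined and the qualifying reading is not kept out of it; if that reading is used, regression to the mean overstates improvement

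*Combined protocol and SAP*

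**What the plan says.** Section 5 (Study Population) aims for 20 patients who "have uncontrolled hypertension (SBP > 130 mmHg and/or DBP > 80 mmHg". It does not give the number, date or setting of the readings that establish this. Section 4 states the design: "This is a pragmatic before and after trial with the patient serving as their own control". Section 7 (Expected Results) holds the only hypothesis with a p-value, that a significantly "greater proportion of patients in the after study period will be in proper control of their hypertension", with control defined as below 130/80 mmHg.

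Section 5 describes the initial visit as a "one-hour in-person appointment at the clinic site, where they will be asked for consent for participation in the study", and Section 6 adds a pre-survey. Neither mentions a blood pressure measurement at that visit. Also in Section 6, the study's "Blood Pressure Device will be given to the patient to monitor blood pressure at home daily", pharmacists are to "Educate the patients on how to monitor their blood pressure", and the contact schedule is "Follow-up with patients once per week for six (6) weeks", each call covering that week's readings. "The total duration of the study will be eight (8) weeks".

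Section 11 (Data Management and Analysis) says that readings are captured automatically in Epic. Mean pressure and the number of patients in control are compared between a pre-period and a post-period, neither of which is defined. It names a two-tailed t-test without saying whether it is paired, and a chi-square test worded for low versus high device compliers.

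**The concern.** Patients are selected on the outcome variable, at the same threshold that defines success, and no control group shows what would have happened anyway. A patient picked on a high reading will on average read lower next time, because part of that reading was chance. If the selecting reading also serves as the before value, this drift counts as improvement in both the control proportion and the mean change.

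Whether blood pressure improves is one of the secondary objectives in Section 3. The primary objective is to produce data for designing a larger study, so an inflated pilot effect could be carried forward. The aims about comfort and data collection do not depend on the before value.

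**Working it through.** **No stated figure to reproduce.** The plan gives no effect size, standard deviation, control rate or power for the 20 patients.

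**Step 1, logic.** Eligible: SBP > 130 or DBP > 80. Controlled: SBP < 130 and DBP < 80. No reading can meet both. If the qualifying value is the before value, baseline control is 0/20, nobody can worsen, and every later value below 130/80 counts as a gain. This needs no assumption.

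**Step 2, changes needed for significance.** With k patients moving into control and none moving out, the exact McNemar two-sided p is 2 × 0.5^k: k = 5 gives 0.0625 and k = 6 gives 0.031. So 6 of 20 are needed.

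**Step 3, size with no treatment effect.** Assumptions not in the documents:
- mean usual pressure in the patients screened: 130/78, 135/81, 140/84 or 145/86
- between-patient SD 12/8 and within-patient SD 8/5 to 12/7
- SBP-DBP correlation 0.6
- after value: the mean of 7 readings, with the same usual pressure as the qualifying reading

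For selection on SBP alone, the expected fall is σw² / √(σb² + σw²) × φ(a) / (1 − Φ(a)), where a = (130 − μ) / √(σb² + σw²). With μ = 130, σb = 12, σw = 8: 64 / 14.42 × 0.798 = 3.5 mmHg. The plan also admits patients on DBP alone, whose SBP need not be high, so the fall is smaller. Simulating the actual entry rule gives 2.5 mmHg for the same inputs.

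Simulated results (2 million patients per scenario; ranges cover the within-patient SDs and whole-number or continuous readings):

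| Usual mean | SBP fall, one qualifying reading (mmHg) | SBP fall, mean of three (mmHg) | Controlled afterwards, one reading | Of 20 | P(6 or more of 20) |
|---|---|---|---|---|---|
| 130/78 | 2.5 to 4.8 | 0.9 to 1.9 | 15.8% to 21.8% | 3.2 to 4.4 | 8% to 26% |
| 135/81 | 1.7 to 3.6 | 0.6 to 1.3 | 9.7% to 13.5% | 1.9 to 2.7 | 1% to 4% |
| 140/84 | 1.1 to 2.5 | 0.4 to 0.9 | 5.3% to 7.6% | 1.1 to 1.5 | at most 0.3% |
| 145/86 | 0.8 to 1.8 | 0.2 to 0.6 | 2.8% to 4.1% | 0.6 to 0.8 | about 0 |

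The last column is the binomial tail with n = 20; for example, p = 0.158 gives 8.3% and p = 0.218 gives 25.8%.

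For the mean change with one reading, a paired t-test shows a significant fall in 25% to 42% of trials at 130/78 and 6% to 9% at 145/86, against a nominal 2.5%. An unpaired t-test does so in 2% to 15% and at most 1%. The bias in the estimate is the same either way.

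**Step 4, sensitivity.** With between-patient SD 9/6 or 15/10, or correlation 0.4 or 0.8, the SBP fall is 0.6 to 5.6 mmHg with one reading and 0.2 to 2.5 with three. With one reading, the McNemar rate is 3% to 42% at 130/78 and at most 6% at 135/81.

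**Step 5, separate baseline.** When the before value is the mean of 7 readings independent of the qualifying one, mean change is 0, before and after control rates agree, the paired t-test rate is 2.4% to 2.7%, and the exact McNemar rate is at most 0.1%.

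**The case against.** The strongest reply is that the plan already generates a usable baseline. Readings are daily and each weekly call discusses that week's values, so home readings should exist before the first call. Automatic capture in Epic and the use of mean readings over periods also point to averaged device data rather than one earlier reading. This largely stands. A reader might infer that the qualifying reading will be the baseline, or that no reading falls between eligibility and counselling; the documents support neither. What remains is that no section assigns those home readings to the before period or excludes the qualifying one. Section 8 could contain a definition, but Sections 5, 6, 7 and 11, where one would be expected, do not.

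The size rests on assumed inputs, and that also stands. If the qualifying reading came from the clinic and the after values from home, a setting difference could add to the artefact or offset it, and the simulation does not model this. Section 2 itself notes that home and office readings are inconsistent.

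A reader might also cite much larger false-positive rates for control: an unpaired chi-square needs only 4 of 20 against 0 of 20 (p = 0.035), which gives 39% to 66% at 130/78 with one reading. Section 11 words chi-square for comparing compliers, and Section 4 makes each patient their own control, so the documents do not establish that this test would be applied to control.

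Finally, this is a pilot, blood pressure improvement is the last of three secondary objectives, and nothing says the pre-post change will be the larger study's effect size. That limits the consequence but does not remove it.

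**Conclusion.** The concern holds conditionally: the plan as written permits a before value that is biased towards improvement. Given that use, 0/20 at baseline follows from the thresholds alone, and the direction of the regression effect does not depend on the chosen inputs. Its size does. Under the main assumptions it is about 0.8 to 4.8 mmHg systolic with one qualifying reading and 0.2 to 1.9 with the mean of three. The risk of a false claim on control is material only if many patients have usual pressures close to the threshold. If the sponsor already intends the early home readings as baseline, the defect is a missing definition and the selection artefact is absent. This is a cheap improvement, not a flaw that undermines the pilot.

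**What to change.** 1. In Sections 7 and 11, state that the qualifying reading is used for eligibility only. Define the before value as the mean of the daily study-device home readings taken after enrolment and before the first weekly telehealth call. Define the after value as the mean of home readings over a window of equal length at the end of the study. Six weekly calls within eight weeks leave about two weeks that Section 6 does not place; the sponsor should reconcile where the windows sit, without changing any clinical management. State that the contrast is counselling added to home monitoring and device education, since both precede or accompany the baseline readings. The device-question calls in Section 12 may overlap the window and should be acknowledged.
2. Analyse as paired data: exact McNemar for control and a paired t-test for mean pressure, each change with a 95% confidence interval.
3. Report that the uncontrolled change still includes other time effects, and do not let it alone supply the effect size for the larger study.

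The cost is protocol wording. The apparent improvement will also be smaller, because the expected baseline control rate is no longer 0% by construction: about 3% to 22% in the one-reading scenarios above, although a sample of 20 may still show none.
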